#### Avoidance of bias

In order to avoid a high proportion of a single ethnic or racial group, we decided to involve multiple high-volume centers across the country. All participating centers will send all clinically indicated data (echocardiograms, CMR, ECG, and Holters) to the respective core laboratory, where the cardiologist will be blind to the assigned group, giving a final interpretation. All 2-week ambulatory ECG Holter monitors will be contracted to a single company (ZioPatch™, IRhythm Technologies, Inc.) and evaluated by the Holter core lab ([name]) to prevent differences in PVC detection algorithms. Finally, stratified randomization will ensure an equal distribution of subjects between PVC burden above and below 20%.

#### Sample size justification.

*This has been estimated solely on primary end-point of improvement in LV ejection fraction after PVC suppression. We are planning to compare the improvement in LVEF between PVC suppression strategies (RFA vs. AADs groups). Due to the multiple random effects, a simulation study was conducted to estimate the number of subjects required for this study. Specifically, data was simulated according to a linear mixed-effects model with an unstructured error structure with a random site effect. It was assumed that subjects would have a LVEF level of 25% (SD=5%) in each of the groups at baseline and LVEF levels of 40% and 35% (SD=10%) in the RFA and AAD groups at 12 months, respectively. A within subject correlation of 0.25 was assumed along with an inter-site standard-deviation of 1%. *This model was fit assuming that, on average, 10% of the subjects would drop out randomly.* Approximately 140 total subjects (70 per group) should be enrolled to reject the null hypothesis that the mean LVEF between RFA and AAD groups are equal with probability (power) 0.8 and Type I error probability of 0.05. *As a pilot study we have determined the need to enroll at least 20% (30 subjects) of preliminary sample size estimation to understand feasibility and key aspects of subject enrollment, randomization and retention to properly power a large-scale randomized PAPS study. Sample size is increased by 15% (6-9 additional subjects, 36-39 subjects total – between 19-20 subjects in each treatment group) to take into account possible spontaneous improvement of LV dysfunction during the 3-month observation period between treatment strategies.**

## **J. Ethical / Regulatory Affairs**

The study will be submitted for review to your IRB of record and registered on clinicaltrials.gov prior to commencement of study activity.

### **Event Adjudication Committee**

We will establish a committee to evaluate each hospitalization event to determine its relationship to HF and/or the PVC suppression treatment arm. The committee consists of three physicians: 2 heart failure cardiologists (Drs. [name] and [name]) and 1 cardiac electrophysiologist ([name]) (see letters of support). Throughout the study and the adjudication process, the committee members will remain blinded to treatment allocation, as well as other information that may disclose allocation (TSH, LFTs).

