c.4. Cardiovascular magnetic resonance (CMR). If clinically indicated, a delayed enhancement CMR will be performed at each center following a single protocol (approved by CMR core laboratory Director: [name], Richmond, VA) and sent to the CMR core lab for final interpretation. Similarly, CMR core lab and participants will remain blinded to group assignment. CMR will be obtained at baseline if clinically indicated to assess LV volumes, mass, ejection fraction, and mid-wall circumferential strain; overall myocardial T1, T2, and extracellular volume fraction (ECV); and scar location and extent using late gadolinium enhanced methods according to previously published techniques. Associations between each CMR assessment and improvement in LV function (responders) will be determined after PVC suppression strategy. Interstitial myocardial fibrosis and outcomes between early- vs. late-coupled PVCs in an attempt to support a mechanistic aim in final PAPS study. The CMR will be considered clinically indicated to exclude other types of cardiomyopathy, and all sites have agreed to order CMR on enrolled subjects.

c.5. Minnesota living with heart failure quality of life (QOL) and NYHA functional class questionnaires to be used in the PAPS study will be approved by [name] (Heart failure core lab). These questionnaires will be provided to each center to be answered by each subject in their local institution. This will allow us to assess heart failure symptoms and change in quality of life and functional status during the observation period and between both treatment groups. Questionnaires will be sent directly to the Heart failure core lab. *All QOL and NYHA questionnaires will be evaluated and graded by an event adjudication committee (independent of the steering committee, see Section G. Ethical / Regulatory Affairs). If clinically indicated, we will request to provide brain natriuretic peptide (BNP) levels as well as CRP and ESR as per schedule on Table 2.* Participants who are evaluated by study staff and suspected to be depressed will be referred to a primary care provider to facilitate the evaluation.

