c. 6. Complications, heart failure admissions and adverse events. *All events* including mortality, hospital admissions and heart failure exacerbations and treatment-related complications will be documented on each subject throughout the observation and treatment periods. Each center will report any adverse events to the Coordinating Center (McGuire VA Medical Center, Richmond VA) within 24-48 hours of the occurrence or knowledge of the event. *All SAE/hospital admissions, procedure complications and events will be evaluated and assigned by an event adjudication committee (see Section G. Ethical / Regulatory Affairs and documents: Human subjects and Data Safety Monitoring plan for details).*

*Participating centers will provide all available clinical data to respective core labs (echocardiogram, cardiac MR and Holter) and Coordinating Center (McGuire VA Medical Center) through REDCap with a case number without identifiers and treatment randomization as outlined in the Manual of Operations and Standard Operating Procedures manual.*

Of note, subject participation and results of this study will not change diagnostic testing (e.g. electrophysiologic studies for other indications) and medical management including medical therapy (unless safety drug interactions are clear) and indicated procedures (e.g. left heart catheterization). ICD implantation is not encouraged (but not prohibited) during the study as the CM may improve or even resolve after RFA of PVCs as recently shown by Penela et al..

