#### **E. Primary and secondary outcome measures.**

*The outcomes are divided in primary and secondary end-points (Table 3).*

*The primary end-points will consist of:*

1. *Improvement of LVEF after PVC suppression at 12-month follow-up.* This is chosen as primary-end point due to the known prognostic value of LVEF. The lower the LVEF, the higher the risk of sudden cardiac death and heart failure. This will compare the overall improvement or change in LVEF between RFA and AAD groups. This end-point will support that either RFA or AADs have an overall better outcome due to significant improvement of LV function with potential impact on morbidity and mortality associated with PVC-CM.

2. *Responders to PVC suppression strategy at 12-month follow-up* (See rationale under Section “Definitions” in 3rd paragraph of Aim 2). Assessment of the number of responders (delta LVEF  $\geq$  10%) after PVC suppression strategies (RFA or AADs) will assess the effectiveness of RFA and AADs to reverse or improve cardiomyopathy induced by frequent PVCs. Evidence that either RFA or AADs is superior to improve or even reverse LV dysfunction in subjects with high burden PVCs could have significant impact of morbidity and mortality including future heart failure and ventricular arrhythmias, and also may avoid ICD implantation.

*The secondary end-points will consist of:*

1. *Efficacy of RFA vs AADs groups to achieve successful PVC suppression at 12-month follow-up, defined as a reduction of PVC burden  $\geq$ 80% (regardless of LVEF change). Understanding the success rate of PVC suppression between RFA and AADs will help better determine the best treatment to those subjects with high PVC burden.*

2. *Composite end-point of adverse events at 12-month follow-up, including worsening in NYHA functional class (I-IV), number of HF and cardiac-related admissions, RFA complications and AAD adverse effects and cardiovascular death.*

This adverse event composite end-point is chosen to understand the overall complications and adverse effects/events related to RFA and AADs. Worsening of NYHA functional class will be defined as when/if the subject’s functional status worsens by one NYHA class. Hospital admissions will be defined as any visit to ED or hospital admissions related only to a cardiovascular event such as heart failure, angina, pre/syncope and palpitations.

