### **Risk Benefit assessment**

All PVC suppression strategies (RFA and AADs), proposed in this grant application are approved by the Heart Rhythm Society and FDA for the treatment of ventricular arrhythmias, respectively. Subjects assigned to the RFA arm may have a small risk of minor or major complications related to RFA of PVCs. However, these risks associated with RFA of PVCs are acceptable and RFA of PVCs continues to be performed in clinical practice even though there is limited data to support benefit from this intervention. Risks associated with RFA are small (1-2%) including but not limited to stroke, myocardial infarction, coronary artery injury, bleeding, cardiac tamponade, pneumothorax, atrioventricular block with subsequent need for permanent pacemaker, and even death. Similarly, antiarrhythmic drugs (AAD) may have long-term risks/adverse effects based on the antiarrhythmic chosen (e.g. amiodarone has significant long-term effects including lung disease such as decrease in lung diffusion capacity, optical neuritis, abnormal thyroid and liver function, and pro-arrhythmic effects; see Section C in Protection of Human Subjects document for details). Yet, these treatment options are currently standard of care frequently offered to this subject population with known complications and these adverse events. To minimize the potential risks with AADs, all subjects should be considered for additional safety laboratory analyses during treatment as recommended per guidelines based on AAD chosen (amiodarone - TSH, LFTs, PFTs, eye exam).

A pregnancy test will be obtained on females of childbearing age that are assigned to the RFA treatment prior to procedure due to fluoroscopy exposure. In contrast, a pregnancy test will be performed on a monthly basis on those randomized to the antiarrhythmic treatment arm to confirm the lack of pregnancy throughout the 12-month follow up period. If a female on antiarrhythmic arm becomes pregnant during the 12-month follow up period, we will consider stopping antiarrhythmics and the subject will be withdrawn from the study.

The IRB should be notified of any serious adverse events (SAE) within 24 hours of such event or knowledge of the event. Additionally, the PAPS National Research Coordinator should be notified within 24 hours of the event or knowledge of the event. The investigator must decide whether each incident meets the definition of a SAE.

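### The adjudication committee must attribute events to RFA or AAD while blinded to arm and denied TSH and LFT results, and the plan does not say whose attribution feeds the adverse-event composite

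*Combined protocol and SAP*

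**What the plan says.** Section J (Event Adjudication Committee) gives a committee of three physicians the task to "evaluate each hospitalization event to determine its relationship to HF and/or the PVC suppression treatment arm". The same paragraph then sets the blind, which applies for the whole trial and during adjudication itself: "the committee members will remain blinded to treatment allocation, as well as other information that may disclose allocation (TSH, LFTs".

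Section C, item c.6, sets a wider task. It covers all SAEs and hospital admissions, and adds that "procedure complications and events will be evaluated and assigned by an event adjudication committee". Item c.5 gives the committee a further job: "All QOL and NYHA questionnaires will be evaluated and graded by an event adjudication committee".

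Section E and Table 3 define the secondary composite of adverse events. Besides NYHA worsening and HF or cardiac admissions, it includes "RFA complications and AAD adverse effects and cardiovascular death". Its stated purpose is "to understand the overall complications and adverse effects/events related to RFA and AADs".

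Section J (Risk Benefit assessment) lists among the long-term effects of amiodarone "optical neuritis, abnormal thyroid and liver function, and pro-arrhythmic effects". Section D makes amiodarone the AAD of choice, and Table 2 schedules TSH and LFT only for subjects assigned to it.

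The Data Safety Monitoring Plan, item a, has the investigator judge whether an adverse event is related to RFA and/or AAD therapy. Section A describes the treatment groups as un-blinded.

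**The concern.** To say that an event was caused by a treatment, one must know which treatment was given and when. The committee is asked for that judgement and denied the information it needs. The two arms are affected differently. A record of a plainly procedural event tells the reader that the subject was ablated, so the blind does not survive it. A thyroid or liver effect of amiodarone is shown by the very tests that are withheld, so the blind survives but the effect cannot be confirmed.

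Hypothesis 3 in the Specific Aims predicts that RFA will have the lower rate of this composite, and the Project Summary and Specific Aims describe a design with blinded end-points. If the committee's assignment is the one that counts, RFA events are recognisable and part of the AAD events are not, which leans the comparison towards AAD. If the investigator's attribution counts, these components are classified by staff who know the arm. Either way, the adverse-event rates that section F intends to carry into the design of the full trial would rest on an unstated rule.

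**Working it through.** The plan states no figure on this point, so the check is mainly a comparison of its rules.

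**1. What each decision needs, against what section J allows.**

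| Component or decision | Information needed | Possible under the section J blind? |
|---|---|---|
| Worsening by one NYHA class | Functional class over time | Yes |
| HF or cardiac admission, and its relation to HF | Clinical record, redacted | Yes |
| Cardiovascular death | Cause of death | Yes |
| RFA complication | Whether and when an ablation took place | No; a plainly procedural record discloses the arm |
| AAD effect, thyroid or liver | Drug given, with TSH or LFT | No; both are withheld |
| AAD effect, other | Drug given | No; allocation is withheld |
| Relation of an admission to the treatment arm | Treatment given and timing | No |

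The problem is confined to the last four rows.

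**2. Whether withholding TSH and LFT can be avoided within the blind.** Table 2 schedules these tests only if amiodarone is assigned, so a scheduled result alone discloses the AAD arm. Section J is right that they unmask. The blind and the evidence therefore cannot both be kept in a single review.

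**3. Which events reach the committee.** Section J covers hospitalizations; item c.6 covers SAEs, admissions, procedure complications and events. An abnormal TSH or LFT found in an outpatient comes to the committee only under item c.6.

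**4. Whether another route is named.** The Data Safety Monitoring Plan gives relatedness to the investigator. Section E and Table 3 do not say whether the composite uses that judgement or the committee's. No section gives the committee an unblinded step.

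**5. Scale, for RFA complications only.** Inputs: 19-20 subjects per group (Sample size justification), and an RFA risk of 1-2% (Risk Benefit assessment) or 2-3% (Data Safety Monitoring Plan, item c). These two ranges differ, so 1-3% is used. All subjects in the arm are assumed to be ablated.

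- Expected number = n × p: 19 × 0.01 = 0.19; 20 × 0.03 = 0.60.
- Chance of at least one = 1 − (1 − p)^n: 1 − 0.99^19 = 0.174; 1 − 0.97^20 = 0.456.

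So 0.19-0.60 complications are expected, with a 17-46% chance of one or more. The documents give no rate for thyroid or liver effects, so no corresponding figure exists for the AAD arm.

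**The case against.** The strongest reply is that a route already exists: the un-blinded investigator attributes adverse events, and section E nowhere says that an AAD effect or RFA complication counts only once the committee confirms it. The first part stands and narrows the point. It does not remove it, because item c.6 has the committee assign these events and nothing says which classification prevails.

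Second, section J alone concerns hospitalizations, so an outpatient laboratory abnormality would not come before the committee. That is correct for section J; it comes in through item c.6, and the two sections differ.

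Third, stroke, myocardial infarction, bleeding, AV block and death are on the list of RFA risks and could occur in either arm. With procedure details removed, such events need not reveal allocation. That stands too: only a plainly procedural event unmasks by itself. But redacted in this way, the event can be classified by type and still not be attributed to the ablation.

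Fourth, the Manual of Operations may settle how records are redacted. It is not among the documents, and item c.6 cites it for data sent to the core laboratories and Coordinating Center, not to this committee.

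Fifth, this is a secondary endpoint in a small pilot, and the Data Sharing Plan says that the data are not meant to settle the comparative benefit of the strategies. That limits the consequences, but section F still wants adverse-event rates from the pilot for planning.

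A reader might go further and infer that the whole composite cannot be adjudicated, or that the blinded end-point design is untrue for the trial. The documents do not support either. NYHA worsening, admissions and cardiovascular death can be judged blinded, and LVEF and PVC burden are read by core laboratories blinded to arm (section C). A reader might also want a count of unconfirmed thyroid and liver events. There is no rate to base one on, and section D permits AADs other than amiodarone, for which these tests are not scheduled.

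**Conclusion.** The concern holds as a conflict between stated rules, limited to the treatment-specific part of one secondary endpoint: RFA complications, AAD adverse effects, and the relation of an admission to treatment. Under the blind as written, these cannot be adjudicated on an equal footing in the two arms, and the plan leaves open whether the committee's or the investigator's classification feeds the composite. The remaining components and both primary LVEF endpoints are not affected. Nor is safety oversight, since the Data Safety Monitoring Plan gives the DSMB full access to study records.

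The number of events affected cannot be computed from the documents. The RFA figures above show only that complications would be few, so a single classification could matter to the reported rate. The conclusion rests on the text of sections C, E and J and the Data Safety Monitoring Plan; an adjudication charter or Manual of Operations could already resolve it, but neither is available. It should be corrected before adjudication begins.

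**What to change.** Reconcile section J (Event Adjudication Committee), section C item c.6 and the Data Safety Monitoring Plan item a, as follows.

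1. **Blinded step.** On redacted records, the committee classifies event type, relation to HF, whether an admission qualifies, and cause of death. These decisions are locked.
2. **Attribution.** Relation to RFA or AAD is assigned in a separate unblinded step with TSH, LFT and procedure records, or is taken from the investigator. State which of the two counts for the composite.
3. **Order.** If the committee does step 2, it does so only after all of that subject's blinded decisions and NYHA and QOL grading are locked. The same members grade those questionnaires to month 12, so unblinding them after a first event would compromise later NYHA grading and later admissions.
4. **Reporting.** State that the RFA-complication and AAD-adverse-effect components are not blinded end-points, and report them separately from the blinded components.
5. **Scope.** State whether the committee reviews hospitalizations only or all events.

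The cost is protocol and charter wording, a short second review of treatment-related events, and a narrower blinded end-point claim. Committee attribution would come late for each subject, but the DSMB need not wait for it. No new visits, tests or subjects are needed.

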### **Risk Benefit assessment**

All PVC suppression strategies (RFA and AADs), proposed in this grant application are approved by the Heart Rhythm Society and FDA for the treatment of ventricular arrhythmias, respectively. Subjects assigned to the RFA arm may have a small risk of minor or major complications related to RFA of PVCs. However, these risks associated with RFA of PVCs are acceptable and RFA of PVCs continues to be performed in clinical practice even though there is limited data to support benefit from this intervention. Risks associated with RFA are small (1-2%) including but not limited to stroke, myocardial infarction, coronary artery injury, bleeding, cardiac tamponade, pneumothorax, atrioventricular block with subsequent need for permanent pacemaker, and even death. Similarly, antiarrhythmic drugs (AAD) may have long-term risks/adverse effects based on the antiarrhythmic chosen (e.g. amiodarone has significant long-term effects including lung disease such as decrease in lung diffusion capacity, optical neuritis, abnormal thyroid and liver function, and pro-arrhythmic effects; see Section C in Protection of Human Subjects document for details). Yet, these treatment options are currently standard of care frequently offered to this subject population with known complications and these adverse events. To minimize the potential risks with AADs, all subjects should be considered for additional safety laboratory analyses during treatment as recommended per guidelines based on AAD chosen (amiodarone - TSH, LFTs, PFTs, eye exam).

A pregnancy test will be obtained on females of childbearing age that are assigned to the RFA treatment prior to procedure due to fluoroscopy exposure. In contrast, a pregnancy test will be performed on a monthly basis on those randomized to the antiarrhythmic treatment arm to confirm the lack of pregnancy throughout the 12-month follow up period. If a female on antiarrhythmic arm becomes pregnant during the 12-month follow up period, we will consider stopping antiarrhythmics and the subject will be withdrawn from the study.

The IRB should be notified of any serious adverse events (SAE) within 24 hours of such event or knowledge of the event. Additionally, the PAPS National Research Coordinator should be notified within 24 hours of the event or knowledge of the event. The investigator must decide whether each incident meets the definition of a SAE.

### **Data Safety Monitoring Plan and Board**

Serious adverse events and subject monitoring will be performed as stipulated in the Data Safety Monitoring Plan (DSMP). As required by NIH, this multicenter trial will also have a Data Safety Monitoring Board (DSMB) that will monitor the safety of the study. The DSMB will consist of 2 heart failure specialists (Drs. [name] and [name]) and a cardiac electrophysiologist ([name]) (see letters of support). Further details of DSMP and responsibilities of IRB and DSMB as stated in the Section: Protection of Human Subjects and Data Safety Monitoring Plan.

